based on EDSS, or worsened patient quality of life, compared to continuers. This could be especially important for those discontinuing natalizumab, where there remains significant concern, and also disagreement, about the potential for not just recurrence of disease activity, but also significant rebound (ie, higher than prior baseline) of disease activity.^{63-65,70} As such, we will perform interim analyses at two pre-specified time points, when 25 (Tables 2, 4 below) and 65 (Tables 3, 5 below) patients in each group have completed their six-month evaluation or achieved the primary endpoint, ie if a participant has an acute relapse at any time, including before the T₁, 6 month safety check, or is noted to have a new or enlarging T2 brain MRI lesion, they will be considered to have achieved the primary endpoint. We would require the DSMB to consider discontinuing the study if either of the following occurred at either interim analysis time point:

- The difference in the proportion of events between the discontinue and continue groups was statistically significantly (alpha = 0.025) greater than 0.10. Presumably the discontinue group would be greater.
- If one group, presumably the discontinue group, had an event proportion statistically significantly (alpha = 0.025) greater than the expected number of cases defined by the continue group.

Primary endpoints will be defined as either:

1. "Relapse" will be defined as the appearance of new neurological symptoms or worsening of pre-existing neurological symptoms lasting at least 48 hours in a subject who had been neurologically stable or improving in the previous 30 days and accompanied by objective change in the neurological examination corresponding to that symptom (worsening of 0.5 point on the EDSS or worsening by 1.0 or more points on the pyramidal, cerebellar, brainstem or visual functional system score). Fatigue or subjective cognitive worsening, alone or in combination, will not be considered a "Protocol defined relapse."

Each Relapse event will be categorized on CRFs as one of the below:

• Protocol defined relapse

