For secondary outcomes AIMS 2-3, a two sample t-test comparing change scores between treatment groups with an alpha level of 0.05 and an effect size equal to 38% of the standard deviation would achieve 80% power, and an effect size of 44% of the standard deviation would achieve 90% power. A two sample proportion difference test between treatment groups with an alpha level of 0.05 and an effect of approximately 0.19 would be able to achieve 80% power, and an effect of 0.22 would achieve 90% power. A relative risk test with an alpha level of 0.05, a control proportion of 0.3

or 0.5, and a ratio of 1.61 or 1.37 respectively would achieve 80% power, and a ratio of 1.71 or 1.42 respectively would achieve 90% power. A Pearson correlation of 0.27, within a group of 112 samples, between two normally distributed variables, would be detectable with 80% power for an alpha level of 0.05, and a Pearson correlation of 0.30 would be detectable with 90% power.

Table 2: Safety Comparisons of the two groups at 25 patients in each group

Sample per Group = 25		
Group	# of Events	Percent
Continue	0	0.00
Discontinue	7	28.00
Proportion		
Difference Estimate	95% Confidence Interval	
0.2800	0.1067	0.4939

Sample per Group = 25		
Group	# of Events	Percent
Continue	1	4.00
Discontinue	10	40.00
Proportion		
Difference Estimate	95% Confidence Interval	
0.3600	0.1311	0.5765

Table 3: Safety Comparisons of the two groups at 65 patients in each group

Sample per Group = 65		
Group	# of Events	Percent
Continue	1	1.54
Discontinue	15	23.08
Proportion		
Difference Estimate	95% Confidence Interval	
0.2154	0.1083	0.3407

Table 4: pValues in Dark Grey
denote statistically significant events
in discontinuers (vertical axis) vs
continuers (horizontal) at interim
analysis of 25 patients in each group.

Sample per Group = 25							
Null Hypothesis for p (Expected # of Events)							
# of Events	0.02 (0.5)	0.04 (1)	0.08 (2)	0.10 (2.5)	0.12 (3)	0.16 (4)	0.20 (5)
1	0.3965	0.6399	0.8756	0.9282	0.9598	0.9872	0.9962
2	0.0886	0.2642	0.6053	0.7288	0.8195	0.9263	0.9726
3	0.0132	0.0765	0.3232	0.4629	0.5912	0.7870	0.9018
4	0.0014	0.0165	0.1351	0.2364	0.3525	0.5837	0.7660
5	0.0001	0.0028	0.0451	0.0980	0.1734	0.3707	0.5793
6	0.0000	0.0004	0.0123	0.0334	0.0709	0.2002	0.3833
7	0.0000	0.0000	0.0028	0.0095	0.0243	0.0920	0.2200
8	0.0000	0.0000	0.0005	0.0023	0.0070	0.0361	0.1091
9	0.0000	0.0000	0.0001	0.0005	0.0017	0.0243	0.0468
10	0.0000	0.0000	0.0000	0.0001	0.0004	0.0035	0.0173

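### The interim count admits patients with early relapses at once but event-free patients only at six months, so the proportions set against Tables 2-5 are biased upward, by an amount that ranges from trivial to material

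*Combined protocol and SAP*

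**What the plan says.** Section III.D (Risks/Safety) plans two interim analyses, held when 25 and then 65 "patients in each group have completed their six-month evaluation or achieved the primary endpoint". It explains that a participant who "has an acute relapse at any time, including before the T₁, 6 month safety check" has reached the endpoint, as has one with a new or enlarging T2 brain lesion.

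The DSMB must consider discontinuing the study under either of two criteria:

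- Criterion 1: the difference in event proportions "was statistically significantly (alpha = 0.025) greater than 0.10".
- Criterion 2: one group "had an event proportion statistically significantly (alpha = 0.025) greater than the expected number of cases defined by the continue group".

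The first look is tied to Tables 2 and 4 and the second to Tables 3 and 5. Table 2 is titled "Safety Comparisons of the two groups at 25 patients in each group" and Table 3 "Safety Comparisons of the two groups at 65 patients in each group". Tables 4 and 5 give p-values for event counts with samples of exactly 25 and 65 per group. Nothing in section III.D or III.F (Data Analysis Plan) names a different interim population, sets an event window for the looks, or provides a time-to-event estimate.

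**The concern.** A binomial proportion needs a denominator chosen without regard to outcome. Take two patients randomised to the same group on the same day. One relapses in month 1 and enters both numerator and denominator immediately. The other stays well and enters neither until month 6. While accrual continues, the set at any look therefore holds some early relapses from recently randomised patients whose event-free contemporaries are still waiting outside. The proportion is not a six-month risk, and it is too high in both arms.

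A second effect comes from the same sentence. A relapse counts "if a participant has an acute relapse at any time", so a patient well past T1 contributes more than six months of exposure, and this grows by the second look.

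At stake is the calibration of the figures the DSMB is given. Tables 4 and 5 are plain binomial tails, and counts produced by this rule do not follow them.

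**Working it through.** **1. The plan's own figures.** Tables 4 and 5 are exact binomial upper tails. In the 0.02 column, P(X ≥ 3 | 25, 0.02) = 0.0132 and P(X ≥ 5 | 65, 0.02) = 0.0098, both as printed. These are the first counts below 0.025 (2 of 25 gives 0.0886; 4 of 65 gives 0.0414).

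**2. Inputs.** From the protocol: n = 25 and 65; entry at the earlier of endpoint and six months; MRI at T1, so MRI-only events normally enter at about month 6 with the event-free patients; relapses found between visits through monthly calls and unscheduled visits. Not in the protocol, so assumed: accrual a = 1.5, 3 or 6 per arm per month, and relapse share of events s = 25-100%. For comparison, 265 patients over an assumed 24-48 months is about 5.5 to 2.75 per arm per month.

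**3. Effect of the entry rule.** Let π be the true six-month risk, with relapse onset uniform over months 0-6 (mean 3). At time T the expected number admitted is n = a[(T − 6) + 3πs], of whom aπ[(T − 6) + 3s] have events. Eliminating T:

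expected proportion = π[1 + 3as(1 − π)/n].

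Relative inflation at π = 0.02:

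| n | smallest (a=1.5, s=0.25) | a=3, s=0.5 | largest (a=6, s=1) |
|---|---|---|---|
| 25 | 1.125×0.98/25 = 4.4% | 4.5×0.98/25 = 17.6% | 18×0.98/25 = 70.6% |
| 65 | 1.125×0.98/65 = 1.7% | 4.5×0.98/65 = 6.8% | 18×0.98/65 = 27.1% |

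Simulation with random arrivals (20,000 runs per setting) agrees: about 5-70% at n=25 and 2-28% at n=65. If every event were an MRI lesion found at T1 (s = 0), inflation would be nil.

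**4. Against the tabulated 0.02 null.** With π = 0.02 and n=25 the proportion becomes 0.0209 to 0.0341. P(X ≥ 3) is then 0.0149 to 0.0522 (up to about 0.053 simulated), against 0.0132. At n=65 the proportion becomes 0.0203 to 0.0254, and P(X ≥ 5) is about 0.010 to 0.025, against 0.0098.

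The planning rate in section III.F is 0.02 within a year, or about 0.01 per six months. At that risk the largest n=25 proportion is 0.01 × (1 + 18×0.99/25) = 0.0171, and P(X ≥ 3) is about 0.009.

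**5. Criterion 2 against the observed continue proportion.** Both arms are inflated, so the effect partly cancels. Simulated false alarms with equal risks, using 0.02 as the reference when the continue group has no events (a convention the protocol does not state):

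| Six-month risk | n | Fixed cohort | Protocol rule |
|---|---|---|---|
| 1% | 25 | 0.1-0.2% | up to 0.6% |
| 2% | 25 | 0.8-0.9% | up to about 2.5% |
| 2% | 65 | 1.7-1.9% | up to about 3.5% |
| 5% | 25 | about 4.7% | about 5-8% |
| 5% | 65 | 8.1-8.8% | 8.3-9.2% |

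**6. Criterion 1.** With equal risks and equal relapse shares both arms are inflated alike, so the difference stays centred on zero. With unequal risks it is stretched. For 5% v 1%, s = 0.75, n=25, a=3: 0.05(1 + 6.75×0.95/25) − 0.01(1 + 6.75×0.99/25) = 0.0628 − 0.0127 = 0.050, against a true 0.040. At a=6 it is 0.0757 − 0.0153 = 0.060. In this setting criterion 2 fires in about 17% (a=3) or 23% (a=6) of runs, against about 10.5%.

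**7. Exposure beyond T1.** This is additional to steps 3-6. With all events relapses at 0.02 per six months, the monthly hazard is about 0.02/6 and the look falls at about T = 6 + n/a. Expected events are about a(0.02/6)T²/2. For a = 3.67 and n=65, T = 23.7 and the count is 3.4, or 0.053 of 65 (simulated 0.051). Over a = 2.75-5.5 the simulated any-time proportion is 0.039-0.040 at n=25 and 0.044-0.059 at n=65. At the second look this is the larger of the two effects.

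**The case against.** The strongest reply is that the sentence in section III.D is a timing trigger and does not state who is analysed. That is correct: the analysis set is inferred from the table denominators and the absence of any alternative. The inference is the natural one, but the protocol could equally be read as silent, which also calls for clarification.

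Counting early relapses is also deliberate. Section III.D raises rebound after stopping natalizumab, and the background cites recurrence 4-28 weeks after cessation. The bias is towards an early signal, the DSMB need only consider stopping, and it includes a biostatistician and reviews data twice a year. All of this stands and limits the severity. It does not make the tabulated p-values apply to the counts.

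The upper figures are corner cases. The 70% needs every event to be a relapse at 6 patients per arm per month; with a quarter relapses, inflation at n=25 is about 5-19% in simulation. More frequent firing under a real difference (step 6) is partly earlier detection of true harm.

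A reader might infer that an arm with more early relapses fills its quota sooner and so brings the look forward. The text does not support this, since both groups must reach the count.

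**Conclusion.** The point holds on the natural reading of section III.D with Tables 2-5: the interim proportions are not six-month risks and are biased upward in both arms. The size rests on assumed accrual and relapse share. The entry rule alone inflates by about 5-70% at the first look and 2-28% at the second, and exposure past T1 adds to this. The clearest consequence is against a fixed tabulated null: a boundary with nominal tail 0.013 can have a true tail of up to about 0.053 when the six-month risk is 2%.

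A reader might infer that the stopping criteria in general raise false alarms. For the entry rule, the calculations do not show this. At equal risks of 1-2%, criterion 2 against the observed continue proportion stays at or below about 2.5% at n=25 and 3.5% at n=65. At 5% risk its error already exceeds 2.5% with a fixed cohort, because an observed control rate is treated as known; the entry rule adds to this at n=25 and hardly changes it at n=65. Criterion 1 is not biased when risks are equal. Nor does the problem reach the final primary analysis, which uses a separate one-year proportion. Severity is low to moderate.

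**What to change.** In section III.D and any DSMB charter, define the set used for both criteria and for Tables 2-5 as the first 25 (then 65) patients randomised to each group whose T1 date plus the 30-day MRI window of section III.C has passed, with or without an event. Count only events up to T1. Patients who withdrew early stay in the cohort, and the text should say how they are counted.

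Report all other events, both those in later-randomised patients and those after T1, to the DSMB in a separate listing at the same look and at its twice-yearly reviews, so that no early signal is hidden.

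The cost is wording and slightly later looks. From n = a[(T − 6) + 3πs], removing early entry delays a look by 3πs months, at most 0.06 months at 2% risk and 0.15 at 5%; waiting for the MRI window adds about one month.

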Patients will overall be randomized in a 1:1 fashion to either continue or discontinue their present DMT. They will be randomized within each site to either the continuation or discontinuation group in blocks of 2, 4 or 6 through simple random sampling. Patients with all forms of MS, RRMS, SPMS and PPMS will be offered participation, and because patients with all forms of progressive disease tend to act in a similar manner with regard to ongoing disease activity, SPMS and PPMS will be merged into a single category, progressive patients, for any subanalysis. Patients within each category, either relapsing or progressive, will also be randomized in a 1:1 fashion to continue or discontinue their DMT, but we will not stratify a certain number of either category of patients for overall participation. All MRI scans will be read locally for safety and clinical purposes, and PIs will communicate any significant MS or non-MS findings to the primary neurologist (should they not be the primary neurologist). Any new lesion documented on the T₁ or T₂ MRI scan will prompt delivery of a notice within 48 hours, to the PI, that the patient has achieved the endpoint of the study, with a description of relevant findings.

In the event of a suspected relapse, the patient will be instructed to contact their physician and the study coordinator at their local site within 48 hours of new symptoms, and come in for an unscheduled visit and relapse evaluation within seven days of symptom onset. Use of corticosteroids will be at the discretion of the patient and the local PI or other physician. Use of systemic steroids to treat MS symptoms will be concluded to be a Protocol defined relapse. As at scheduled visits, the determination of a relapse at an unscheduled visit will be made by the blinded EDSS examiner, who will perform the EDSS and only then receive information about recent clinical history.

D. Risks/Safety:

A Data Safety Monitoring Board (DSMB consisting of three board-certified neurologists not otherwise associated with the study and biostatistician) will be employed to perform twice yearly reviews of the data and certify that it is acceptable for the study to continue. It is possible that, in spite of a prolonged period with no new inflammatory disease activity, those who discontinue their DMTs will have a substantial increase in inflammatory disease activity, or progressive disease

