A relapse seen within 7 days of onset, independently and blindly observed as a change in EDSS by the Examining Clinician. This relapse is defined as: the appearance of a new symptom or worsening of an old symptom, attributable to MS; accompanied by a change in the neurologic examination attributed to those symptoms (defined as worsening of 0.5 point on the EDSS or worsening by 1.0 or more points on the pyramidal, cerebellar, brainstem or visual functional system scores); symptoms lasting at least 48 hours in the absence of fever; and preceded by stability or improvement for at least 30 days. Any use of systemic steroids to treat MS symptoms will be counted as a Protocol defined relapse, regardless of when the patient was seen.

• Out of window relapse

Same as a protocol defined relapse, except that the patient was not seen within the 7-day window.

• Suspected relapse

Relapse that fails to meet the above situations, but may have been a relapse –i.e. all circumstances point to a relapse, but upon examination by the examining physician, no residual or change in the EDSS is noted.

• Not a Relapse

Pseudo-relapse, ie a worsening of pre-existing neurological symptoms in the context of any significant stressor, including, but not limited to, infection, or physical, psychological or mental stress, as determined by the treating physician; or other symptoms felt not to be related to MS

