their primary neurologist for consideration of restarting a MS DMT of their choice, or switching to an alternative DMT (if they were in the continuation arm). They will continue to be followed at all study time points with all procedures. This is a pragmatic trial, so individuals will continue to receive care from their primary neurologist (in many cases, this will be the Treating physician/PI as well). At all times, it will remain the choice of the patient and their physician to maintain or change the MS DMT. Any worsened neurological symptoms attributed to MS that are treated with systemic steroids, regardless of characterization above, will be counted as a Protocol defined relapse. In this context, it is imperative that patients contact the local PI of the study first and foremost, so that decisions about the use of steroids may be made by study personnel, and steroids used or not used after the determination of relapse status per the protocol.

An adverse event (AE) is the appearance or worsening of any undesirable sign, symptom, or condition occurring after starting the study even if the event is not considered to be related to study conditions or assignment. Study conditions or assignment includes assignment to continue or discontinue prior DMT. Medical conditions and diseases present before starting the study are only considered AEs if they worsen after starting the study. Abnormal laboratory values or test results constitute AEs only if they induce clinical signs or symptoms, are considered clinically significant, or require therapy.

The occurrence of AEs should be sought by nondirective questioning of the patient at each visit during the study. Adverse events also may be detected when they are volunteered by the patient during or between visits or through physical examination, laboratory test, or other assessments. All AEs must be recorded in the AEs eCRF with the following information:

1. the severity grade (mild, moderate, or severe)
2. its relationship to the study drug(s) (suspected/not suspected)
3. its duration (start and end dates or if continuing at final examination)
4. whether it constitutes a serious AE (SAE)

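### The relapse component of the primary endpoint is not fully blinded: steroid treatment alone makes a Protocol defined relapse, and no planned analysis separates those events

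*Combined protocol and SAP*

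**What the plan says.** **Blinding.** The end of section II says that observers of relapses, MRI changes and the EDSS are blinded. In III.C, "the determination of a relapse at an unscheduled visit will be made by the blinded EDSS examiner", and III.E gives that examiner the final assessment of Protocol defined relapse. III.E also says that the patient and the Treating Physician/PI are not blinded.

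**Relapse definition.** III.D requires that symptoms be "accompanied by objective change in the neurological examination corresponding to that symptom", with stated EDSS or functional system thresholds. It then says "Each Relapse event will be categorized on CRFs as one of the below": Protocol defined, Out of window, Suspected, or Not a Relapse. Only the first enters the primary outcome.

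**Steroid rule.** It appears in III.C and twice in III.D. Under the Protocol defined category: "Any use of systemic steroids to treat MS symptoms will be counted as a Protocol defined relapse, regardless of when the patient was seen". Later in III.D, MS worsening that is "treated with systemic steroids, regardless of characterization above, will be counted as a Protocol defined relapse". On who decides, III.C says: "Use of corticosteroids will be at the discretion of the patient and the local PI or other physician". III.D asks that patients contact the local PI first, with "steroids used or not used after the determination of relapse status per the protocol".

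**Pseudo-relapse.** The Not a Relapse category covers worsening in the context of a stressor such as "infection, or physical, psychological or mental stress, as determined by the treating physician".

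**Analyses.** The secondary relapse analyses in III.D add Out of window and Suspected relapses to the Protocol defined ones. III.D also lists steroid-treated MS relapse among serious adverse events and plans proportions, intervals and between-group tests for adverse events. III.F contains no analysis by steroid use.

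**The concern.** The steroid rule bypasses the blinded assessment. An episode that the examiner would class as Suspected or Not a Relapse becomes a primary event once steroids are given for MS symptoms, and the people who decide on steroids know the arm. The trial is open-label, tests non-inferiority and expects few events, so a reader of the result would want to know how many events arose this way.

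The effect could run in either direction. Extra discontinue-arm events make non-inferiority harder to show; extra continue-arm events make a false claim of it easier. An episode matters only in a patient with no new or enlarging brain MRI lesion, because such a lesion already makes the patient an event.

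The pseudo-relapse wording is a smaller matter. It names an unblinded physician within a classification that the rest of the plan gives to the blinded examiner.

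**Working it through.** **Step 1: the passages side by side.**

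| Question | Answer in the plan | Place |
|---|---|---|
| Who makes the final relapse call? | Blinded examiner | III.E |
| Who decides on steroids? | Patient, local PI or other physician | III.C |
| Are the patient and PI blinded? | No | III.E |
| Does steroid use override the category? | Yes | III.D |
| Does it apply outside the 7-day window? | Yes | III.D |
| Is the steroid decision meant to follow the relapse call? | Yes, as a request | III.D |
| Is there an analysis separating steroid-treated events without blinded change? | None | III.D, III.F |

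The request on sequence reduces the exposure. It does not remove it, because the override still applies after the examiner has made the call.

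**Step 2: reproduce the plan's power.** Inputs from III.F: 112 per arm, event proportion 0.02 in both arms, margin 0.08, one-sided alpha 0.025, likelihood-based interval. With i discontinue and j continue events, and l the binomial log-likelihood:

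- z(i,j) = sign(i/112 − j/112 − 0.08) × √{2[l(i/112, j/112) − max over p of l(p + 0.08, p)]}. Non-inferiority is shown if z ≤ −1.96, that is, if the 95% upper limit is below 0.08.
- P(non-inferiority) = Σ over passing (i,j) of Bin(i; 112, pD) × Bin(j; 112, pC).

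At 0.02 vs 0.02 this gives 94.95%, matching the stated 95%. The score method replaces z by (i/112 − j/112 − 0.08)/√{[p̃D(1 − p̃D) + p̃C(1 − p̃C)]/112}, with p̃ the estimates restricted to a difference of 0.08. It gives 90.7%.

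**Step 3: how many events decide the result?** Expected events per arm: 0.02 × 112 = 2.24.

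| Discontinue vs continue | Upper limit, likelihood ratio | Upper limit, score |
|---|---|---|
| 2 vs 2 | 0.0405 pass | 0.0470 pass |
| 4 vs 2 | 0.0670 pass | 0.0727 pass |
| 5 vs 2 | 0.0793 pass | 0.0847 fail |
| 6 vs 2 | 0.0913 fail | 0.0965 fail |
| 3 vs 0 | 0.0680 pass | 0.0758 pass |
| 4 vs 0 | 0.0810 fail | 0.0882 fail |

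From 2 vs 2, reversal takes 6 − 2 = 4 extra discontinue-arm events by likelihood ratio, or 5 − 2 = 3 by score. From 3 vs 0, one is enough.

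**Step 4: the other direction, as illustration only.** Take true proportions 0.10 vs 0.02, the plan's null, and add k spurious continue-arm events, so that (i, j + k) is judged. The value of k is an assumption.

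| k | False non-inferiority, likelihood ratio | Score |
|---|---|---|
| 0 | 2.9% | 1.9% |
| 1 | 4.5% | 3.2% |
| 2 | 6.7% | 5.2% |

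**Step 5: what the planned rate contains.** III.F applies 0.02 to the disease event, which is a Protocol defined relapse and/or a new brain MRI lesion. By the III.C and III.D rules, Protocol defined relapse already includes steroid-treated worsening. The 0.02 therefore includes such events, and the 95% power holds with the rule in place if 0.02 is right.

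**The case against.** **The rule is deliberate.** III.A wants a sensitive marker for a safety question, and counting steroid-treated episodes serves that aim. This stands, and it is why the rule should stay in the primary endpoint.

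**Safeguards exist.** The MRI component is read centrally and blinded. III.D asks that steroid decisions follow the relapse determination. The serious adverse event reporting will show steroid-treated relapses by arm, which indicates a likely ceiling on steroid-only events. All of this stands. What remains is that these reports are not split by whether the blinded examiner found a qualifying change.

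**A reader might infer that the rule costs power.** Adding steroid-only events to 0.02 would lower the computed power, but Step 5 shows that this counts them twice. The documents do not support a loss.

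**A reader might infer that the result is fragile to a single such event.** That is true only next to the decision boundary, where any single event decides, including an MRI lesion. From the expected 2 vs 2 it takes three or four, all in one arm.

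**A reader might infer that the treating physician can remove primary events by calling them pseudo-relapses.** III.E gives the final call on Protocol defined relapse to the blinded examiner, and the phrase may mean only that the treating physician judges the stressor. This is a wording conflict to reconcile, not a demonstrated loss of events.

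**Conclusion.** The point holds in a limited form. As written, an unblinded steroid decision can override the blinded examiner for the relapse component of the primary endpoint, and no planned analysis shows how often this happens. That is at odds with the statement in section II that relapse observers are blinded. It does not make the whole endpoint unblinded, and it does not establish bias in a known direction.

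The size cannot be estimated, because the documents give neither the number of steroid-only events nor their split by arm. The bounds from the plan's own inputs are four one-sided discontinue-arm events (likelihood ratio) or three (score) to reverse 2 vs 2, and one event nearer the margin. The rise in false non-inferiority from 2.9% to 4.5% or 6.7% (likelihood ratio) rests on an assumed one or two extra continue-arm events. The pseudo-relapse wording is a minor clarification. Overall this is a cheap improvement of minor to moderate priority.

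**What to change.** Change endpoint classification only; care stays as it is.

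1. In the Not a Relapse definition in III.D, attribute the pseudo-relapse determination to the blinded Examining Clinician, made after the EDSS, instead of to the treating physician. State that this examiner assigns the CRF category, and record the steroid rule as a separate flag so that it no longer overwrites that category.
2. Keep the steroid rule in the primary endpoint. Flag patients who qualify only through steroid use: no blinded EDSS or functional system change meeting the III.D thresholds at any relapse evaluation, whatever its timing, and no new or enlarging brain MRI lesion. Leaving timing out of the flag means that a late but blindly confirmed relapse is not recoded.
3. Report the number flagged by arm. Repeat the primary non-inferiority analysis with these patients counted as non-events, using the same 0.08 margin, interval method and denominators.

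**Cost.** One wording change, one CRF flag and one sensitivity run. Table 1 already schedules concomitant medication at every visit and monthly call, and EDSS at every scheduled and unscheduled visit. III.C shows that some patients may have finished before this protocol version, so their events need retrospective flagging from recorded EDSS and medication data. Some steroid-only events may be true relapses, so the recoded result belongs in a sensitivity analysis only.
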